## Randomisation

Young people will be allocated to their trial arm status after their eligibility check but before their initial assessment (see Figures 2 and 3, above). A random stratified allocation

[figure not shown]
 <https://www.corc.uk.net/outcome-experience-measures/core-measurement-tools/>

 <https://www.corc.uk.net/outcome-experience-measures/short-warwick-edinburgh-mental-wellbeing-scale-swemws/>

procedure will be used. Random numbers will be generated separately for each stratum allowing UASCs to be assigned to treatment as they enter the study, using the random number function within the R statistical programming software package. Different random number seeds will be used for each stratum and we propose to generate blocks of random numbers of size 6, i.e. 3 in the treatment arm and 3 in the control arm. This procedure will reduce the risk of randomly generated long run sequences of allocation to any one of the groups, potentially upsetting the balance between numbers in the treatment and control groups. The random number allocation will generate the allocation lists with a 50 : 50 probability of assignment to treatment and control for moderate-risk strata.

For high risk strata, a probabilistic allocation rate of 0.64 will be assigned to treatment group, with a corresponding probability of 0.36 to the control group. This higher probability of assignment to treatment group for high-risk cases has been requested by BRC to ensure fewer high-risk cases are held back from receiving the treatment than are moderate risk cases. In addition, BRC retain the right of over-riding allocation to group for cases deemed to necessitate immediate treatment. It is possible that some of the high-risk cases identified at referral could be converted to low-risk after initial assessment. Similarly, some cases initially identified as moderate risk could be converted to high-risk. Young people will remain allocated to their strata and analysis will treat them as intention-to-treat on the basis of their original allocation. The implications of the override are further discussed below under the sensitivity analysis.

Figure 5: CONSORT diagram

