## Design

Table 3: RCT design details

|   |                                |  |
|---|--------------------------------|--|
| Trial type and number of arms            |                                | Non-blinded parallel two-armed randomised control trial with UASC individually randomised to a treatment or waitlist control group (on rolling basis)  |
| Unit of randomisation                    |                                | Young person   |
| Stratification variables (if applicable) |                                | Overall, 6 strata will be used, comprising of one high-risk stratum and five moderate risk strata defined by the British Refugee Council locations, which include four with physical geographical boundaries and a fifth with virtual boundaries. Allocation rates are 50 : 50 for UASCs in moderate risk strata and 66: 34 in high risk strata. |
| Primary outcome                          | Variable                       | Continuous variable – scores ranging from 0 to 40  |
|   | Measure (instrument, scale)    | Mean intervention group YP-CORE score compared to mean control group YP-CORE score collected at endline (3 months from start of intervention) by delivery staff i.e. therapists  |
| Secondary outcome(s)                     | Variable(s)                    | Continuous variable – scores ranging from 7 to 35  |
|   | Measure(s) (instrument, scale) | Mean intervention group SWEMWBS score compared to mean control group SWEMWBS score collected at endline (3 months from start of intervention) by delivery staff i.e. therapists  |

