### Sample Size / Minimum Detectable Effect Size Calculations

Table 4: Minimum Detectable Effect Size Calculations

|  |               |           |
|--|---------------|-----------|
| MDES (Proportion of a Standard Deviation)  |               | 0.24      |
| Proportion of Variance in Outcome Explained by Covariates  (R  ) | Child         | 0.5       |
|  | Family        | NA        |
|  | Social Worker | NA        |
| Intraclass Correlations Coefficient (ICCs)   | Family        | NA        |
|  | Social Worker | NA        |
|  | Team          | NA        |
| Alpha  |               | 0.05      |
| Power  |               | 0.8       |
| One-Sided or Two-Sided?    |               | Two-sided |
| Level of Intervention Clustering   |               | NA        |
| Average Cluster Size (if Cluster-Randomised)   |               | NA        |
| Sample Size  | Intervention  | 145       |
|  | Control       | 135       |
|  | Total         | 280       |

 This includes, and will most likely be most influenced by, a baseline measure of the outcome.

 By default we would recommend two-sided tests.

The sample size is determined through the resources available to deliver the intervention. Consequently, we have calculated the MDES based on the expected achieved sample sizes, a stratified random allocation design at the level of the UASC and the availability of a baseline measure, which assumes a pre-post correlation of 0.71, (i.e.  $R^2 = 0.5$ ). The PowerUp tool was used to calculate the sample size, using the BIRA2\_1f spreadsheet with 6 strata (4 local and 1 virtual Local Authority for low risk cases and one stratum for high risk cases) and an average block size of 47 to be allocated evenly to treatment and control groups.

It is assumed that 88% of the 280 cases will be moderate risk, i.e. 247 cases. These will be allocated 50: 50 to treatment and control, i.e. 123.5 cases per trial arm. Of the 12% assumed to be high risk (n = 33), it is assumed that 66% will be allocated to treatment (n = 22) and 34% to control (n = 11). Overall, 145 cases will be allocated to the treatment group and 135 to the control group, i.e. 52% of total cases will be in the treatment group.

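### The high-risk allocation rate is stated two ways with its blocking left open, and a single fixed, published block of six makes some moderate-risk allocations foreseeable

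*Protocol*

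**What the plan says.** **High-risk rate.** Table 3 (Design) states: "Allocation rates are 50 : 50 for UASCs in moderate risk strata and 66: 34 in high risk strata". The Sample Size section uses the same rate: 33 of 280 cases are high risk, 22 go to treatment and 11 to control, and the arm totals are 145 and 135. The Randomisation section states "a probabilistic allocation rate of 0.64 will be assigned to treatment group, with a corresponding probability of 0.36 to the control group".

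**Blocking.** The Randomisation section states "Random numbers will be generated separately for each stratum allowing UASCs to be assigned to treatment as they enter the study". It then says that seeds differ by stratum and, in the same sentence, "we propose to generate blocks of random numbers of size 6, i.e. 3 in the treatment arm and 3 in the control arm", with no exception for any stratum. The paragraph closes by describing "allocation lists with a 50 : 50 probability of assignment to treatment and control for moderate-risk strata". High-risk cases follow in a new paragraph with their own rate and no mention of blocks.

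**Setting.** Table 3 describes a "Non-blinded parallel two-armed randomised control trial" with rolling entry, and its five moderate-risk strata are the delivery locations. Under Inputs, Leeds, Birmingham and the remote service have one therapist each. Under Activities, an administrator of the delivery organisation checks eligibility and a high-risk assessment is made at that stage. Allocation follows the eligibility check. In Table 10 the evaluator develops the randomisation tool and leads the first randomisation, and the protocol is uploaded in that same week. The protocol does not say who can see the lists or past allocations, and it names only one block size.

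**The concern.** There are two separate matters.

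The first is a contradiction in the operative text. Whoever programs the high-risk list finds two rates. The list could be drawn in permuted blocks or by independent draws, and nothing says which. The stated purpose of blocking is to avoid long runs to one arm. If the high-risk stratum is unblocked, that protection is missing in a stratum of only 33.

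The second is allocation concealment. With a fixed, known block size, the end of each block can be worked out from its beginning. In this trial the arm is visible, because a young person either starts therapy or joins the waitlist, and at three locations one therapist could follow nearly the whole sequence. Someone who foresees the next arm can influence when a case enters, or whether it is classed as high risk and so moves to a list that favours treatment. The resulting imbalance in prognosis would be only partly removed by adjusting for baseline YP-CORE and stratum. The intention-to-treat rule protects against departures after allocation, not against selective entry before it.

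**Working it through.** **Inputs.** From the Sample Size section and Table 4: 247 moderate-risk and 33 high-risk cases, R² = 0.5, two-sided alpha 0.05, power 0.8. From the Randomisation section: 3:3 blocks of six.

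**1. Arm totals.** Treatment total = 247/2 + 33p, where p is the high-risk probability of treatment.
- p = 0.66: 123.5 + 21.78 = 145.28, leaving 134.72. This reproduces 145 and 135.
- p = 0.64: 123.5 + 21.12 = 144.62, leaving 135.38. This also rounds to 145 and 135.
- Difference: 33 × 0.02 = 0.66 of a case.
- For comparison, 3:3 blocks in the high-risk stratum would give 16.5 and 16.5, and totals of 140 and 140.

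**2. Minimum detectable effect size.** The blocked-design formula is (t₀.₉₇₅ + t₀.₈₀) × √[(1 − R²)/(P(1 − P)N)]. With N = 280, P = 0.52 and 267 degrees of freedom it gives 0.238, which reproduces the stated 0.24. To let the rate differ by stratum, replace P(1 − P)N with 247 × 0.25 + 33p(1 − p) and use normal quantiles:
- p = 0.66: 2.80 × √(0.5/69.16) = 0.2382
- p = 0.64: 2.80 × √(0.5/69.35) = 0.2379
- p = 0.50: 2.80 × √(0.5/70.00) = 0.2368

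All three round to 0.24.

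**3. What blocks can deliver in the high-risk stratum.** A block of six gives neither 0.64 nor 0.66. The nearest split, 4:2, gives 0.667. Exact 0.64 needs blocks of 25 (16:9). Exact 0.66 needs blocks of 50 (33:17), more than the whole stratum. The protocol's own 22 and 11 are exactly 2:1. If the list is instead 33 independent draws at 0.64, the number treated has mean 21.1 and a binomial 95% range of 16 to 26.

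**4. Foreseeable allocations in a 3:3 block.** An allocation is certain once the other arm of its block is full, so the certain allocations are the final run of one arm. Of the 20 possible blocks, 12 end in a run of one, 6 in a run of two and 2 in a run of three:

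(12 × 1 + 6 × 2 + 2 × 3)/20 = 30/20 = 1.5 of 6 = 25%.

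The closed form for a block of 2m agrees: 2m/(m + 1) = 6/4 = 1.5. Over the moderate-risk strata this is 0.25 × 247 = 61.75, about 62 cases, ignoring incomplete final blocks. An observer who always guesses the arm with more places left is right 4.1 times in 6, or 68.3%.

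**The case against.** The strongest reply on the first matter is that little is wrong. The 64/66 conflict moves less than one case and has no effect on power. The stratum indicators in the primary model already allow for a different treatment probability in the high-risk stratum. That is correct, and the rate conflict is a specification fault, not a power fault.

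Three stronger readings are tempting, and the protocol does not support them.
- A reader might infer that the whole scheme cannot be built. The five moderate-risk lists, 247 of 280 cases, can be built as described. Only the high-risk list is stuck.
- A reader might infer that 3:3 blocks are imposed on the high-risk stratum. The block sentence has no exception, but the paragraph then confines 50:50 lists to moderate-risk strata and a new paragraph gives high-risk cases their own rate. The more natural reading is that 3:3 does not apply there. What remains is silence on whether that stratum is blocked at all.
- A reader might cite the sample-size remark about even allocation as a further conflict. It describes an input to the power tool, where a block is a stratum averaging 47 cases, and is not a rule for building lists.

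On the second matter, the reply is that certainty needs the block size, the block boundaries and every earlier allocation in the stratum. The evaluator leads the randomisation, and referrals also come from outside agencies and young people themselves. This stands in part: the 25% is conditional on that knowledge, and it is not an estimate of bias. But central list-holding does not stop staff from working out the end of a block from visible past allocations and a published size, and no other concealment safeguard is stated.

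**Conclusion.** The concern holds in two limited parts.

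1. The high-risk rate is contradictory (66:34 against 0.64:0.36) and the blocking of that stratum is unspecified. The high-risk list cannot be generated until this is settled. The numerical effect of the rate conflict is about 0.7 of a case.

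2. The fixed, published block of six is an avoidable weakness in concealment. About a quarter of moderate-risk allocations would be certain in advance to anyone who knew the block size and the stratum's earlier allocations. The assumptions are 3:3 blocks run from a known start and complete knowledge of past allocations. The protocol does not establish that staff have that knowledge. The unblinded rolling design, site-based strata and single-therapist locations make it plausible. How much bias would follow cannot be calculated from the protocol.

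Both parts should be corrected before the first randomisation.

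**What to change.** - State one high-risk rate in Table 3, the Randomisation section and the Sample Size section. The protocol does not show which figure was agreed with the delivery organisation, so this needs confirming. Permuted 2:1 blocks would reproduce the protocol's own 22 and 11.
- Say explicitly how the high-risk stratum is blocked, and limit 1:1 blocks to the five moderate-risk strata.
- Replace the fixed block of six with randomly varied sizes, for example 4, 6 and 8. Taken singly, a block of 4 is more predictable than one of 6 (2m/(m + 1) gives 1.33 of 4, or 33%) and a block of 8 is less so (1.6 of 8, or 20%). The gain comes from the observer not knowing which size is running. The net reduction has not been calculated.
- Keep block sizes and lists with the evaluator and out of any document that delivery staff can see, including the published protocol, and state this.

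The cost is a few lines in the allocation script, short edits to three sections and slightly looser balance at the end of recruitment. The planned sample size and analysis model stay as they are.

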## Participants

### Intervention locations

The evaluation will include all four delivery sites of the British Refugee Council in:

- London
- Kent
- Birmingham
- Leeds

In addition to this, the evaluation will include an online/remote delivery ‘site’.

The British Refugee Council will be responsible for communicating with delivery sites about the evaluation and how this will impact delivery (compared to business as usual). The evaluation team will join a training session in May 2021 to assist with these communications.

### Eligibility criteria

The eligible population must meet the following criteria:

- **Young people who are legally defined as UASC** – young people who have arrived in the UK alone without parents or guardian and are in the care of Local Authorities. The British Refugee Council supports young people regardless of the status of their asylum claim (not yet made, pending, granted). They accept young people who have applied for asylum or have had asylum granted.
- **Aged 18 years or under at time of referral:** While new referrals must be 18 or under at time of referral, the Council will continue support for those who’ve had their 18th birthday.
- **Passed initial assessment** – this is a collaborative decision to determine whether the intervention is an appropriate pathway. For some complex cases, the British Refugee Council will work with stakeholders and consider further referrals.

### Sample Size / Minimum Detectable Effect Size Calculations

Table 4: Minimum Detectable Effect Size Calculations

|  |               |           |
|--|---------------|-----------|
| MDES (Proportion of a Standard Deviation)  |               | 0.24      |
| Proportion of Variance in Outcome Explained by Covariates  (R  ) | Child         | 0.5       |
|  | Family        | NA        |
|  | Social Worker | NA        |
| Intraclass Correlations Coefficient (ICCs)   | Family        | NA        |
|  | Social Worker | NA        |
|  | Team          | NA        |
| Alpha  |               | 0.05      |
| Power  |               | 0.8       |
| One-Sided or Two-Sided?    |               | Two-sided |
| Level of Intervention Clustering   |               | NA        |
| Average Cluster Size (if Cluster-Randomised)   |               | NA        |
| Sample Size  | Intervention  | 145       |
|  | Control       | 135       |
|  | Total         | 280       |

 This includes, and will most likely be most influenced by, a baseline measure of the outcome.

 By default we would recommend two-sided tests.

The sample size is determined through the resources available to deliver the intervention. Consequently, we have calculated the MDES based on the expected achieved sample sizes, a stratified random allocation design at the level of the UASC and the availability of a baseline measure, which assumes a pre-post correlation of 0.71, (i.e.  $R^2 = 0.5$ ). The PowerUp tool was used to calculate the sample size, using the BIRA2\_1f spreadsheet with 6 strata (4 local and 1 virtual Local Authority for low risk cases and one stratum for high risk cases) and an average block size of 47 to be allocated evenly to treatment and control groups.

It is assumed that 88% of the 280 cases will be moderate risk, i.e. 247 cases. These will be allocated 50: 50 to treatment and control, i.e. 123.5 cases per trial arm. Of the 12% assumed to be high risk (n = 33), it is assumed that 66% will be allocated to treatment (n = 22) and 34% to control (n = 11). Overall, 145 cases will be allocated to the treatment group and 135 to the control group, i.e. 52% of total cases will be in the treatment group.

The MDES is a standardised effect size, i.e. it is measured in standard deviation units. This is advantageous when dealing with power analysis when outcome measure summary statistics such as the mean and standard deviation are unknown. We are not aware of reliable studies showing the distribution of the YP-Core among the population of interest studied here. However, to give an example of the MDES, a recent study by O'Reilly et al (2016) showed a mean score of 18.3, with a standard deviation of 7.6 among a sample of children aged 12-16 engaging for the first time with an intervention. Using these scores for illustrative purposes only, an MDES of 0.24 multiplied by the SD of 7.6 gives a score of 1.8. Given a control group mean of 18.3, we would require the intervention to produce a YP-Core mean score of 20.1, or above, in the treatment group to be detected using our design.

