## Summary

The My View therapeutic intervention for unaccompanied asylum seeking children (UASC) will be delivered by the British Refugee Council for 11 months between June 2021 and May 2022. It will be delivered by trained therapists in four physical (London, Kent, Birmingham, Leeds) locations and one therapist will operate remotely. In total, 280 UASC aged c. 12 to 18 at the start of the intervention will take part. My View contains either one to one therapeutic intervention over 12 one-hour long sessions (to be accessed by c. 190 young people), group therapy (to be accessed by c. 57 young people) or crisis intervention (to be accessed by c. 33 young people). The therapeutic interventions are supported by individual case work for each client, where relevant. For the purpose of the evaluation, the intervention period is 3 months.

The primary aim of the intervention is to improve the psychological and emotional wellbeing of UASC. The primary outcome measurement will be the YP-CORE, which will measure psychological distress at baseline and follow-up 3 months later. The secondary outcome measurement will be SWEMWBS, which will measure mental well being at the same time points as the YP-CORE.

The three elements of the evaluation are a randomised controlled trial, an implementation and process evaluation and a cost analysis. The evaluation will take place from June 2021 to June 2022.

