## Activities

The young person's eligibility for the intervention is checked by a Refugee Council administrator. If eligible, the young person's details are entered into a Refugee Council database and an assessment of whether the young person is 'high risk' is carried out.

There are three ways in which therapists conduct direct work with clients:

**Crisis sessions.** Up to three of these are offered to clients with urgent immediate need for therapeutic support, classified as 'high risk'. If necessary, clients will be offered follow-on one to one therapeutic support. Therefore, they cannot be randomised as they will bypass the waitlist. Activities taking place in crisis intervention include stabilisation through grounding, explanation of symptoms, and drawing on internal strengths.

**Up to 12 one to one sessions,** or until there is a collaborative ending agreed before 12 sessions. These sessions last an hour each. The majority of clients will engage on a weekly basis, however may miss appointments throughout their intervention due to conflicting schedules (e.g. Home Office, college – beginning at college, termly timetable changes, social worker visits etc.), religious practices (e.g. Ramadan), sleep disturbances and other factors. This is why it takes longer than 12 weeks to complete the average intervention. For the purpose of the evaluation, a cut-off period of 3 months has been agreed to collect the follow-up measure. The structure and content of the 12 sessions is outlined in Table 2.

**Group sessions.** There is a minimum number of six (6) and maximum of 12 participants per group session. Group sessions are offered weekly, and attendance varies.

The format of general group sessions is as follows (and content outlines in Table 2):

- 'check-in' – gauging energy and mood levels,
- 'warm-up' activity to foster participation and engagement,
- 'main activity' – this can be a series of group exercises or one extended group activity,
- 'debrief' – to reflect or comment on activity and
- 'check-out' – to close and reflect on any take away learning etc.

The average length of engagement is 4.5 months. For the purpose of the evaluation, a cut-off point of 3 months has been agreed. We will randomise until January 2022, at which point the 'final' control group members will start receiving My View for 3 months (until April 2022).

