## Analysis Plan

### Primary Analysis:

The primary and secondary impact analysis will use regression models to establish impact. For the primary outcome, the YP-CORE summary score will be the outcome variable. A binary indicator identifying whether the UASC was allocated to treatment (scored as unity) or control (scored as zero) will be included as a main effect in the model. The coefficient for this variable will carry the impact effect as the average difference in the YP-CORE outcome between the treatment and control group. The coefficient will be significance tested with a two-tailed alpha of  $P < 0.05$ , to establish the significance of the impact effect. Additionally, further variables will also be included in the regression, including the baseline measure of YP-CORE and an identifier for the stratification group. A single level OLS regression model with an identity link and Gaussian error term, will be used, given the lack of clustering in the data and the continuous nature of the YP-CORE outcome score.

$$\hat{Y} = a + bD + \sum_j^J z_j X_j + e \quad (1)$$

Where  $\hat{Y}$  is the predicted outcome score,  $a$  is the intercept,  $b$  is the coefficient carrying the impact effect,  $D$  is the binary indicator equalling unity for the treatment group and zero for the control group, and  $z_j$  represents coefficients for the baseline measure and the 5 stratum group indicator variables, with  $X_j$  representing the baseline score and the binary indicator variables for the 5 stratum indicator variables, and  $e$  is assumed to be normally distributed.  $J$  runs from 1 to 6, with 1 representing the mean centred baseline score and 2-6 the 5 stratum indicator variables. The excluded 6th stratum will be represented in the intercept.

Residuals from the regression model will be checked for heterogeneity and adjusted using a Huber-White approach, if required. Checks for heterogeneity will include a visual inspect of the plot of the residuals against the fitted values and Leven tests.

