## Missing Data

We anticipate that the baseline YP CORE questionnaire will be completed by all at the initial assessment interview, given the importance of the baseline in the analysis anyone not completing will be excluded from the analysis. Similarly, we anticipate the questionnaire measures of secondary outcomes to be collected at that same time. The endline primary outcome measures will be collected three months after starting the intervention with attempts

---

made to collect intermediate YP-CORE scores at the 6-week interval (for the treatment group only).

We anticipate that the key risks to missing data will arise with the endline outcome score. Cases without an endline score will not be imputed and will be dropped from the analysis, which will be run using complete case response data only. BRC routinely attempt to collect YP-CORE data after the first six weeks but only for the treatment group. Consequently, we cannot treat both groups equally with respect to missing endline data, so will not attempt to use the 6-weekly score for imputation purposes.

If there is evidence of differential attrition between the treatment and control groups in terms of socio-demographic characteristics, we will construct a weight to account for differential attrition and include a weighted version of the primary and secondary outcomes in the sensitivity analysis to check on the stability of the impact estimate.

If there is no evidence of differential attrition, no weighting will be undertaken.

It is possible, however considered highly unlikely, that young people may give partial responses to the baseline and/or outcome data and, if this occurs, item responses may be imputed to enable a more complete summary score.

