### Ethical considerations relating to the RCT

#### The use of randomisation is justified in this context

Previous evaluation of My View has not employed a robust comparison (a counterfactual), which means that we cannot be confident about causality when claims about positive impacts are made. We are in 'equipoise' meaning we are agnostic on whether the

programme is effective or not, making an RCT the logical next step, taking the evidence to the next level.

Well-planned and executed RCTs can establish that programmes lead to particular benefits for UASC, rather than other factors explaining changes. This evaluation therefore has the potential to provide the highest quality evidence to help inform future commissioning and practice.

The randomisation has been designed so as to exclude UASC who are deemed as requiring 'crisis intervention'. After the initial one to three sessions of crisis intervention, young people will not be returned to the waitlist, however, they will continue to receive treatment (if they so wish, in line with therapists' availability) immediately.

Further, at initial assessment, if a young person has been randomised to the waitlist group and the therapists believes them to require crisis intervention, the random allocation can be overwritten.

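### The protocol contradicts itself on whether high-risk and crisis cases are randomised, and the MDES of 0.24 rests on the favourable reading with no stated allowance for loss

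*Protocol*

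**What the plan says.** All references are to the Protocol.

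**Text that keeps crisis cases out of randomisation**
- The Summary gives 280 participants in total, made up of about 190 in one-to-one therapy, about 57 in group therapy, and "crisis intervention (to be accessed by c. 33 young people").
- Activities describes crisis clients as urgent cases classified as high risk, and adds: "Therefore, they cannot be randomised as they will bypass the waitlist".
- The list of procedures under Intervention and Theory of Change marks crisis sessions as outside the evaluation.
- The ethics section justifying randomisation says: "The randomisation has been designed so as to exclude UASC who are deemed as requiring" crisis intervention. It then allows the allocation to be overridden when a waitlisted young person is found at initial assessment to need crisis intervention.

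**Text that randomises and models a high-risk group**
- Table 3 sets six strata, one of them high-risk, with an allocation favouring treatment. Randomisation repeats that design and keeps each case in its original stratum and arm for an intention-to-treat analysis.
- The sample-size section takes 88% of 280 (247) as moderate risk and says of the rest: "Of the 12% assumed to be high risk (n = 33), it is assumed that 66% will be allocated to treatment (n = 22") and 11 to control. That gives 145 and 135 in Table 4.
- Primary Analysis fits five indicator variables for six strata.

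**Text on who is analysed**
- Missing Data excludes anyone without a baseline score and says: "Cases without an endline score will not be imputed and will be dropped from the analysis".
- The risk register rates drop-out without post-data as medium likelihood and high impact. No attrition rate or allowance appears anywhere.
- The worked example states that "an MDES of 0.24 multiplied by the SD of 7.6 gives a score of 1.8".

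**The concern.** The two groups of statements do not fit together. On one, the 33 crisis cases in the 280 never enter the randomisation. On the other, 33 high-risk cases are a randomised stratum and count towards the sample behind the MDES. A reader cannot tell whether the trial's effect estimate covers high-risk young people, or whether the model has five strata or six.

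The MDES depends on the answer. The 280 is the delivery total, and it is entered as if every one of those young people were both randomised and analysed. If fewer are, the trial's sensitivity is lower than stated, and a null result would be judged against a figure that the design does not reach.

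**Working it through.** **Inputs.** Table 4 gives R² = 0.5, power 0.8, alpha 0.05 two-sided, and 145 + 135 = 280. Primary Analysis agrees on the test: "The coefficient will be significance tested with a two-tailed alpha of" 0.05. The sample-size section names a blocked individual-assignment design with six strata. The illustrative SD is 7.6.

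**Formula.** MDES = (t₀.₉₇₅ + t₀.₈₀) × √[(1 − R²) / (P(1 − P)N)], where P is the share allocated to treatment and df = N − number of strata − 1 covariate − 1. Power for 0.24 comes from the noncentral t distribution.

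**Step 1: reproduce the plan's figure.**
- N = 280, P = 145/280, df = 272.
- Standard error = √[0.5 / (0.24968 × 280)] = 0.0846.
- MDES = (1.969 + 0.843) × 0.0846 = 0.238, or 0.238 × 7.6 = 1.8 points. Power for 0.24 is 81%.
- The plan's approximation of 6 × 47 = 282 cases, split evenly, gives 0.237.

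Both round to 0.24. A one-sided test (0.210) or no covariate (0.336) does not match. The stated figure is therefore the two-sided one with all 280 cases analysed.

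**Step 2: compare the counts.** 190 + 57 + 33 = 280, so the Summary without its crisis cases leaves 190 + 57 = 247. The sample-size section gives 247 moderate-risk and 33 high-risk cases. The two splits are numerically identical.

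**Step 3: MDES if the 33 are not randomised.**
- N = 247, five strata, P = 0.5, df = 240.
- Standard error = √[0.5 / (0.25 × 247)] = 0.0900.
- MDES = (1.970 + 0.843) × 0.0900 = 0.253, or 0.253 × 7.6 = 1.9 points. Power for 0.24 is 76%.

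With five strata and equal allocation, 264 analysed cases are needed for the MDES still to round to 0.24, so 247 falls short with no loss at all.

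**Step 4: loss.** The Protocol gives no rate. The rates below are assumptions, shown only to indicate the range.

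| Randomised | Assumed loss | Analysed | MDES | Points (SD 7.6) | Power for 0.24 |
|---|---|---|---|---|---|
| 280 | 0% | 280 | 0.238 | 1.8 | 81% |
| 280 | 5% | 266 | 0.244 | 1.9 | 79% |
| 280 | 10% | 252 | 0.251 | 1.9 | 76% |
| 280 | 20% | 224 | 0.266 | 2.0 | 71% |
| 247 | 0% | 247 | 0.253 | 1.9 | 76% |
| 247 | 10% | 222 | 0.267 | 2.0 | 71% |
| 247 | 20% | 198 | 0.283 | 2.2 | 66% |

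**The case against.** The strongest reply is that the operative design text randomises a high-risk stratum throughout: Table 3, Randomisation, the sample-size section, Primary Analysis and Sensitivity Analysis. On that reading 280 are randomised and 0.24 is right. The Protocol also partly separates high risk from crisis. The ethics section excludes those needing crisis intervention, not everyone at high risk, and it lets a waitlisted case later found to need crisis intervention be randomised first and then overridden. This stands. It is why the point is a contradiction to be reconciled, and why the documents do not show that the stated sensitivity is definitely missed.

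A reader might also infer that the 33 crisis cases and the 33 high-risk cases are the same people. The identical number and the definition in Activities suggest it, but no sentence states it.

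The phrase about expected achieved sample sizes could mean that 280 is already net of loss. That is weak, because 280 is also the full number due to take part in delivery according to the title table and the Summary. The risk register does list mitigations, including tracking through the referrer and monthly contact with the waitlist. It also names the session 6 score as a fall-back, but Missing Data declines to use that score for imputation.

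The sample size is set by delivery resources, so no recruitment decision turns on the MDES, and dropping the 33 alone moves it only from 0.238 to 0.253. That limits the size of the point but does not remove it.

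**Conclusion.** The contradiction is real, and the MDES of 0.24 holds on only one of the Protocol's two readings. The arithmetic itself is correct; what is open is the N put into it. If the 33 are not randomised, the MDES is 0.253 and power for 0.24 is 76%. That result uses the Protocol's own R², alpha and power and needs no assumption about attrition.

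If all 280 are randomised, the figure survives a loss of up to about 5% (0.244 still rounds to 0.24) and not much more. A reader might infer from the table that the true MDES is 0.27 to 0.28. The documents do not support that as a finding, because it needs both the 247 reading and assumed losses of 10% to 20%. What can be said is that no allowance for loss is stated while the analysis is complete-case.

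The weight of the point lies in the unclear randomised population and in a sensitivity figure that may be somewhat too favourable, not in a large loss of power.

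**What to change.** 1. Reconcile the Summary, the procedures list, Activities, Table 3, Randomisation, the sample-size section, Primary Analysis and the ethics section into one statement. It should say which risk groups are randomised, how crisis and high-risk cases relate to each other, and how many strata the model has. Which clinical rule applies is for the trial team to decide.
2. Restate Table 4, the arm sizes and the points example on the expected randomised and analysed N. For 247 with no loss the MDES is about 0.25.
3. Add loss scenarios labelled as illustrative assumptions: 247 with 10% or 20% loss gives 0.27 or 0.28; 280 with 10% or 20% loss gives 0.25 or 0.27.

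The cost is protocol wording and a slightly less favourable MDES. No extra recruitment is asked for.

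One separate date conflict can be settled in the same revision. Activities has randomisation running until January 2022, when the final "control group members will start receiving My View for 3 months (until April 2022"), whereas the ethics section offers controls the intervention three months after randomisation. This does not itself change the MDES and is not part of the point above.
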